#### 7.1.6 EQ-5D-5L (Quality of Life)

The EQ-5D-5L is a generic instrument to measure HRQoL, and validated for several modes of administration (in-person, phone, mail). It consists of five dimensions (mobility, self-care, usual activities, pain/discomfort, anxiety/depression) with five possible levels for each dimension, describing the severity of problems in the specific dimension experienced today (*EQ descriptive system*): no problems, slight problems, moderate problems, severe problems, extreme problems.

The EQ-5D-5L is applicable to a wide range of health conditions and treatments and provides a single index value derived from the severity of problems in the five dimensions. It takes only a few minutes to complete.

Additionally, the EQ-5D-5L includes a visual analogue scale (*EQ VAS*), a thermometer-like rating scale ranging from 0 (worst imaginable health state) to 100 (best imaginable health state). Participants are asked to mark their current overall state of health on the scale.

#### 7.1.7 Questionnaires for the health economic evaluation

The efficacy outcome of "PICTURE-Economics" is the *incremental cost-effectiveness ratio*. To assess the incremental cost-effectiveness ratio, two measures, one for costs, one for effects, are necessary.

Costs will be assessed by means of a modified (shortened) German version of the Client Sociographic and Service Receipt Inventory (CSSRI) (Chisholm et al., 2000). This questionnaire considers the resource utilization for inpatient services, outpatient physician services, outpatient therapeutic services, medications as well as formal and informal care. Additionally, the questionnaire captures productivity losses caused by absenteeism. Resource utilization will be monetarily valued by means of administrative and market prices according to the German manual for standardized unit costs by Bock et al., 2015). Absenteeism will be valued according to the human capital approach by means of gross hourly wage plus non-wage labor costs.

**QUALYs**: As measure of effects, we will use QALY, a composite measure consisting of the duration of life multiplied by a measure of preference-based HRQoL. In this study, the EQ-5D-5L index values will be employed (Herdman et al., 2011).

#### 7.1.8 Covid-19 Burden Scale

The Covid-19 burden scale is a 10 item questionnaire adapted from Brailovska and Margraf 2020. It includes questions regarding the place of residence, elevated risk (elderly, immunosuppression, comorbidities), exposure to Covid-19, quarantine, feelings of fear or restriction, information and media usage, activities of daily life, healthcare utilization. This questionnaire was deployed in March 2020 at the beginning of the Covid-19 pandemic at T0, T1 and T2 interviews in order to account for effects due to the pandemic and lockdown measures.

#### 7.2 Time schedule of Measurements

All visits and telephone calls will be performed according to the table 'Schedule of Activities and Assessments' (section 2) and the flowchart in Figure 1.

#### **8** Statistical Methods

#### 8.1 Planned Statistical Analyses

#### 8.1.1 Analytical steps

- 1) Data cleaning and curation (completeness, plausibility, outliers, etc.)
- 2) Dropout analysis
- 3) Analysis of baseline data
  - a) Descriptive analysis of all relevant clinical and sociodemographic characteristics, as well as outcome variables at baseline
  - b) Cross-sectional exploratory analysis
- 4) Analysis of primary and secondary outcomes at primary endpoint T1
  - a) Descriptive analysis, comparison of group differences
- 5) Longitudinal analysis
  - a) Descriptive analysis of primary and secondary outcomes throughout observation period
  - b) Calculation of multivariate statistical models from baseline to the primary endpoint T1 for primary and secondary outcomes
  - c) Calculation of multivariate statistical models from baseline to the secondary endpoint T2 for primary and secondary outcomes

#### 8.1.2 Analysis of the primary efficacy endpoint

Primary efficacy endpoint is the absolute change in the PDS total severity score from baseline at month 6 ( $\Delta_6$ PDS := PDST1 – PDST0). By default, the mode of administration is a self-administered paper-based version. For patients who did not complete and send back the paper-based patient questionnaire (non-responding survivors), the PDS-5 total score was assessed during the telephone survey T1, scheduled 6 months after randomization.

The null hypothesis H0:  $G_{NET}(x) = G_{iTAU}(x)$  and  $K_{NET}(t) = K_{iTAU}(t)$   $(0 < t \le T)$ 

is that the treatment groups NET and iTAU will not differ with respect to the distributions of the observed outcome measure  $\Delta_6 PDS$ , whereas  $G_i(x)$  is the cumulative probability distribution of the observed change in PDS severity scores at T1 in group i (i = NET or iTAU), and the distribution of times of death (most likely cause of missingness),  $K_i(t)$  is the cumulative distribution of informative event times in group i.

The null hypothesis will be tested using a two-sample t-test. The null hypothesis can be rejected if the two-sided *p*-value related to the test statistic for the treatment effect is equal to or smaller than the significance level  $\alpha$ =0.05 (two-sided).

Due to an expected high drop-out rate from death in critically ill patients, the nonparametric Lachin method was initially planned as the primary analysis, which is a modified version of the Wilcoxon-Mann-Whitney U-test with a worst rank approach for missing data. However, results from an interim report showed relatively low drop-out rates and a normal distribution of the main outcome variable ( $\Delta_6 PDS$ ). We have consequently decided to update the SAP, replacing the originally planned nonparametric test with a regular two-sample t-test. This change is made to align with the observed normal distribution characteristics of the main outcome variable. The t-test is more suitable for normally distributed data and will provide more accurate estimates of the treatment effect compared to nonparametric tests.

The principal analysis will be performed according to the intention-to-treat (ITT) principle, and unadjusted for screening or baseline covariates or site. The significance level is set to alpha = 5% (two-sided).

Missings prior to the time of the follow-up measurement will occur because of an informative, disease-related event (e.g. death, morbidity) and for other reasons (e.g. non-responders at follow-up measurements T1, T2, loss to follow-up, consent withdrawn). To address the impact of several missingness mechanisms (MAR; MNAR) sensitivity analyses will be performed, e.g. by inverse probability weighting, mixed effect models assuming MAR ("all observed data approach") using the whole observed PDS profile of the surviving patient; multiple imputations techniques; or even complete case analyses using ANCOVA (absolute change score as response variable, treatment group as covariate, adjusting for the baseline score value) for responding survivors until T1.

Moreover, we plan sensitivity analyses in the per protocol population, using linear mixed effects models to explore the role of covariates where indicated (e.g. age and gender, GP-related factors, Covid-19 pandemic effects).

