	• EQ-5D-5L visual analogue scale (VAS); descriptive system: validated self-complete version on paper at T0, validated telephone interview version at T1, T2					
	Disability (WHODAS 2.0, 12-item version)					
	PAM-13 (Patient Activate)	vation Measure)				
	
 
modified version of CSSRI: interview version (assessed by the GP at T0; telephone interview version at T1 and T2)
 
					
Statistical Rationale	Primary efficacy analysis:					
	The primary efficacy endpoint is the absolute change in PDS total severity score ( $\Delta_6$ PDS) from baseline (T0) at month 6 (T1), no matter if derived from the PDS-5 questionnaire administered by mail or phone at T1.					
	The combined null hypothesis for the primary efficacy endpoint at T1 is that distributions of absolute change score values are the same for NET and iTAU in patients with and without missing scores. Under the					

alternative hypothesis, we expect a shift in distributions with a clinically relevant standardized effect size in the order of 0.36 (Cohen's d). To test the null hypothesis of the confirmatory principal analysis, we will use a two-sample t-test assuming a normal distribution of the  $\Delta_6 PDS$  variable. The principal analysis will be performed according to the intention-to-treat (ITT) principle, unadjusted for baseline covariates or site. The significance level is set to alpha = 5% (two-sided). The confirmatory principal analysis will be verified using multivariate models adjusting for sociodemographic factors, drop-out and potential confounders.

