# 6 Randomization and Blinding

Concealed randomization to both treatments (NET; iTAU) is performed with a 1:1 allocation ratio. The trial statistician will remain blinded to randomization codes throughout the course of the trial, i.e. until the study database has been finalised and locked for the final analyses after LPLV.

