8.5 Exclusion Criteria for Patients

Patients will not be included in the study if any of the following criteria applies:

General Exclusion Criteria:

- Patient not able to give written informed consent
- Patient without legal capacity who is unable to understand the nature, scope, significance and consequences of this clinical trial
- Patient has insufficient understanding of the German language
- Patients with a physical or psychiatric condition which at the investigator's or the GP's discretion may put the subject at risk, may confound the trial results, or may interfere with the patient's participation in this clinical trial
- Known or persistent abuse of medication, drugs or alcohol as assessed by GP

Indication specific exclusion criteria:

- Major depression PHQ-9 Score ≥ 23 (referral to specialist care)
- Acute suicidality (diagnosed by GP; referral to specialist care)
- Life expectancy < 9 months
- Concomitant therapy: already receiving another psychotherapeutic trauma therapy such as EMDR or CBT at baseline
- Medication: any neuroleptic, anticholinergic or anti-epileptic drugs

Key exclusion criteria at T0:

- Cognitive dysfunction: MoCA < 24
- PTSD symptoms: PDS-5 Score > 50 (referral to specialist care)

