9.1 Randomization procedure and allocation concealment

All patients together with their GP who give consent for participation and who fulfil the eligibility criteria (both on the patient- as well as on the GP-level) will be randomized after all recruitment and screening activities are completed. This includes confirmation of PTSD diagnosis by the treating GP of the trial participant, together with baseline assessment at T0.

Randomization of the patients is requested no later than 2 weeks after baseline visit at T0.

The randomization number consists of a consecutive three-digit tracking number. The identification number results from a combination of the regional trial centre number and a tracking or screening number.

Concealed randomization to both treatments (NET; iTAU) will be performed with a 1:1 allocation ratio. The allocation sequence will be generated by an independent person affiliated to the ‘Randoulette team’ of the Institute for Medical Informatics, Biometry and Epidemiology (IBE) of the University of Munich who is not involved in assessing the outcomes of the study. The investigators (at the study site) and the GP will be informed about the treatment arm to which his patient is allocated (randomization unit: patient). Neither the investigator, the patient, the GP (including the practice staff), the study personnel including the biometrician, nor the interviewers affiliated to the ITC at the Institute of General Practice, University of Munich, can get access to the randomization list. The randomization is based on a permuted balanced block design with random block length. The procedure considers stratification by study site.

The IBE will provide the internet-based randomization tool ‘Randoulette’ (<https://wwwapp.ibe.med.uni-muenchen.de/randoulette/>) which assigns a specific treatment (NET vs. iTAU) when a new patient and the corresponding GP fulfils the inclusion criteria. In this way, an immediate registration and randomization of enrolled participants is guaranteed.

Since neither the patient, nor the GP can be blind to the allocated treatment, emergency unblinding of single patients is not applicable in this trial.

The RTC will inform the GP practice about the respective allocation status (NET vs. iTAU) after randomization via an official letter and ask the GP to inform the participating patient.

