15.3 Sample size calculation

We performed sample size calculations and additional simulations to detect a clinically relevant and empirically justified effect with respect to the PDS-5 total severity score (range 0-80 points).

Planning figures

Calculation of the reliable change index for previous NET trials indicates that a drop of about 25% (e.g. 23% in (Jacob, Neuner, Maedl, Schaal, & Elbert, 2014)) in the baseline score is a threshold that reflects a reliable change. To achieve mean baseline scores of about 40 points in this score, a mean change of at least $0.25 \times 40 = 10$ points would be necessary. Since post-ICU patients suffer from severe multiple medical conditions (SMOOTH data, (Schmidt et al., 2016)), a more conservative assumption of 60% was assumed for a minimum clinically important difference (MCID), resulting in a study arm mean difference of 6 points in PDS total score at T1.

A sample size of 131 patients (GPs) in each group (i.e., 262 patients in total) will have 80% power to detect a probability of 0.400 that an observation in Group NET is less than an observation in Group iTAU using a Wilcoxon (Mann-Whitney) rank-sum test with a 0.05 two-sided significance level (Software used: nQuery Advisor® 7.0).

The probability of $P(X_{\text{NET}} < X_{\text{iTAU}}) = 0.4$ was calculated with a presumed normal distribution – a difference in means ($\mu_{\text{iTAU}} - \mu_{\text{NET}}$) of 6 points and a common standard deviation of about 17 points – and an effect size of 0.36.

To address the properties of the complex (non-parametric worst rank score) analysis approach, we decided to randomize an additional 78 patients (+ ~30% (=39/131)). Thus, the sample size **to be allocated** to the trial is $N = 2 \times 170 = 340$ patients (GPs) in total.

In accordance with ICU/ regional study center commitments, 3000 patients can be screened, of which N=1000 (33%) are expected to show posttraumatic symptoms (Parker 2015). N=650 (65%) are expected to be willing to participate (patients and GPs) (SMOOTH: 20% non-participants; however, NET is more intense, therefore the rate of non-participation is expected to be higher in this trial), N=550 (~85%) to be screened by the treating GP 3 months post ICU (SMOOTH mortality after 6 months: 18%), N=400 (~70%) to meet inclusion criteria, and N=340 (85%) to consent to study participation at T0.

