We assume a 30% drop out rate from T0 to T1 (primary analysis), and a 15% drop out rate from T1 to T2 (secondary analyses).

Simulations to validate the results of the sample size planning:

Using Lachin’s strategy (Lachin, 1999) will result in analyses of all patients randomized. This is one intention of the ITT principle. However, this comes at the price of attrition due to missing values. To overcome this power-loss we have added another 30% to the original sample size. This choice was evaluated via a small simulation study by varying the number of patients per study arm to support our planning figures: for each setting we performed 10,000 replications and varied the study arm size from 100 to 170 per study arm (1:1 allocation). The results of the simulations to check for a sufficient sample size are displayed in the following figure:

[figure not shown]

Figure 2 Results of the simulations to validate the sample size planning.

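### The confirmatory t-test on PDS-5 change adjusts for neither the baseline score nor the randomisation stratum (site); adding both costs almost nothing and can only help precision in large samples.

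*SAP*

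**What the plan says.** The primary endpoint is PDS-5 at T1 minus PDS-5 at T0. SAP section 8.1.2 tests it with a two-sample t-test at two-sided 0.05 and adds: "The principal analysis will be performed according to the intention-to-treat (ITT) principle, and unadjusted for screening or baseline covariates or site". The protocol had the same rule in section 15.1.1 for the worst-rank Wilcoxon test that the t-test replaced.

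On allocation, protocol section 9.1 says: "The procedure considers stratification by study site". Section 7.2 plans six centres and allows more.

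Adjusted analyses appear only in supporting roles:

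- SAP synopsis: "The confirmatory principal analysis will be verified using multivariate models adjusting for sociodemographic factors, drop-out and potential confounders". Neither the T0 score nor site is named.
- SAP section 8.1.2: an ANCOVA of change on treatment and baseline score, for responding survivors, as one item in a list of example sensitivity analyses. Site is not included.
- SAP section 8.1.1, step 5b: multivariate models from baseline to T1, with no covariates listed.
- SAP section 8.6: a comparison of adjusted and unadjusted models, with no model specified.

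Among the secondary endpoints (SAP section 3.5), EQ VAS is taken at T1 and T2 with no baseline term, although the SAP synopsis shows that it is collected at T0.

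**The concern.** Three things are given up.

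1. **Precision from baseline.** If the within-arm slope of T1 on T0 is not 1, the change score carries baseline variation that a fitted slope would remove.
2. **Protection from chance imbalance.** A baseline difference between arms enters the estimate multiplied by (1 - slope).
3. **The benefit of stratifying.** Balancing arms within site lowers the true variance of the difference if sites differ. An analysis without site does not credit this, so its standard error is somewhat too large and the test somewhat conservative.

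No planned analysis names both terms, and none with either term is confirmatory. If the adjusted and unadjusted results fall on different sides of 0.05, the plan makes the less precise one decisive. The rule may also have outlived its reason: a rank test with tied worst ranks for missing values has no simple adjusted form, whereas a t-test extends directly to a linear model.

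**Working it through.** **Inputs from the documents.** Difference 6 points and "a common standard deviation of about 17 points" (protocol 15.3); 318 randomised, about 159 per arm (SAP 4.1); assumed drop-out to T1 of 30% (protocol 15.3), which leaves 318 x 0.7 / 2 = 111 per arm; T0 PDS-5 at least 20 and not above 50 (protocol 8.4, 8.5); six sites (protocol 7.2). SAP 8.1.2 calls observed drop-out relatively low without a figure, so 111 and 159 bracket the case.

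**Assumptions.** The SD of 17 is taken as the SD of change, because the SAP synopsis attaches the 0.36 effect size to the change score. Baseline SD, slope and site variance are not given.

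**The plan's own figure.** Noether's formula for the Wilcoxon test with probability 0.4 gives N = (1.960 + 0.842)² / [12 x 0.25 x (0.4 - 0.5)²] = 261.6, or 131 per arm. Adding 39 gives 170. The stated sample size reproduces. For the t-test now planned (6/17, noncentral t), power is 88.0% at 159 per arm and 74.5% at 111.

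**Baseline SD.** A normal distribution with mean 40 and SD 17, cut to 20-50, has SD 8.17. A uniform distribution on 20-50 has SD 30/√12 = 8.66. The SD cannot exceed 30/2 = 15.

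**Baseline adjustment.** With within-arm slope b, Var(change) = residual variance + (1 - b)² x SD0². Fitting the slope removes the second term, so the proportional reduction is (1 - b)² x SD0² / 17². Example: b = 0.5 and SD0 = 8.66 give 0.25 x 75 / 289 = 6.5%. Power below uses SD = 17 x √(1 - reduction), with 6 degrees of freedom deducted.

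| Slope b | Variance reduction | Power, 159 per arm | Power, 111 per arm |
|---|---|---|---|
| 1 | 0 | 88.0% | 74.5% |
| 0.8 | 0.9-1.0% | 88.3-88.4% | 74.9% |
| 0.5 | 5.8-6.5% | 89.8-90.0% | 76.9-77.2% |
| 0.2 | 15-17% | 92.5-93.0% | 81-82% |

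At SD0 = 8.66, slopes of 0.8, 0.5 and 0.2 correspond to T0-T1 correlations of 0.38, 0.25 and 0.11.

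**Chance imbalance.** The standard error of the T0 difference is 8.66 x √(2/159) = 0.97 points. A one-SE imbalance leaves 0.97 x (1 - b) = 0.19, 0.49 and 0.78 points in the unadjusted estimate at slopes 0.8, 0.5 and 0.2, against a target of 6.

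**Site.** With a share ICC of the variance due to site and balance within sites, the unadjusted standard error is too large by 1/√(1 - ICC): 1.010 at ICC 0.02 and 1.026 at 0.05. True type I error is 2 x [1 - Φ(1.96 x ratio)] = 4.8% and 4.4%.

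**Both together.** A simulation (4,000 trials, six sites balanced 1:1, ICC 0.03, slope 0.5, uniform T0 on 20-50, 159 per arm) gave power of 88.5% unadjusted and 91.4% adjusted, with type I error of 4.4% and 4.9%. The Monte Carlo standard error of the power is about √(0.885 x 0.115 / 4000) = 0.5 points. A separate run gave 89.1% against 91.4%, and 4.8% against 5.1%.

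**Cost in degrees of freedom.** One for the T0 score and five for six sites. The critical t at 159 per arm moves from 1.9675 (316 df) to 1.9676 (310 df). With slope 1 and no site effect, the loss is about 0.01 percentage points of power.

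**The case against.** **An unadjusted t-test is a legitimate primary analysis, stated openly and consistently in both documents.** This stands. Nothing here makes the test invalid.

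**The gain may be close to nil.** This also stands as a possibility. Entry limits narrow T0 but not T1, which pushes the slope up for a given correlation. With SD0 8.66 and change SD 17, the variance reduction is 2% or less for correlations of about 0.38 to 0.55. Outside that band it returns: 10% at 0.2, and 15% at 0.7, where the slope is 1.77. The documents do not say where this trial lies. Slopes above 1 bring gain as well, so the direction of the argument is unchanged.

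**The 17 may be the SD of the T1 score.** Protocol 15.3 does tie the 6 points to the T1 score. On that reading, with SD0 8.66, a correlation of 0.5 gives slope 0.98 and no baseline gain. A correlation of 0.3 gives slope 0.59 and a variance reduction of about 5%.

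**Baseline adjustment is already planned as a sensitivity analysis.** True, but site is named nowhere, and the question is which analysis decides.

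**It is late to change the test again.** Recruitment closed on 31 December 2022 and T1 falls 6 months (± 3 weeks) after T0, so nearly all primary outcomes were due by the July 2023 SAP. The outcome distribution had already been seen in an interim report. A second change has a credibility cost, and protocol section 20.4 may call for an ethics opinion. These points argue for careful documentation. They do not remove the case for the change, because the SAP says: "The trial statistician will remain blinded to randomization codes throughout the course of the trial".

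**Conclusion.** The point holds, as one of efficiency only. The confirmatory t-test is unbiased and, if anything, slightly conservative. A linear model with T0 score and site targets the same mean difference, and its large-sample variance under 1:1 allocation is no greater.

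For slopes from 1 down to 0.2, the gain from baseline runs from zero to about 5 points of power at 159 per arm (88.0% to 93.0%) and about 7 at 111 (74.5% to 81.8%). Site adds little: at ICC 0.03, about one point at 159 per arm. These sizes rest on an assumed baseline SD of 8.2-8.7, a change SD of 17 and assumed slopes and ICCs. The trial's own data must supply the true values. The recommendation does not depend on a large gain, because the loss in the least favourable case is negligible.

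**What to change.** Before unblinding, amend SAP section 8.1.2 and the synopsis so that:

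- the confirmatory analysis is a linear model of PDS-5 change (T0 to T1) on treatment, T0 PDS-5 score and randomisation site, two-sided alpha 0.05;
- the unadjusted t-test is reported as supportive;
- a rule for pooling sites with few patients is fixed in advance, since extra centres are allowed;
- the exploratory secondary scores use the same form, with T0 EQ VAS as covariate for EQ VAS.

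No new data are needed: T0 PDS-5 is an eligibility score and site is known at randomisation. The statistical cost is about 6 degrees of freedom. The administrative cost is a short SAP amendment and, if section 20.4 of the protocol is judged to apply, an ethics committee opinion. Because the confirmatory test was already replaced once after an interim report, the amendment should carry a date, a reason and a statement that treatment codes were not known. On the SAP's dates (July 2023, planned last visit 31.12.2023, blinding until database lock) there was time to do this.
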